#### ABI=Acquired brain injury; AE=Adverse event; AROM=Active range of motion; EQ-5D 5L=European Quality of Life 5 Dimensions; FU=Follow-up; GSC=Guided Self-rehabilitation Contract; Inj=AbobotulinumtoxinA injection; LL=Lower limb; MFS=Modified Frenchay Scale; SF-12=Short Form 12; TT=Treatment target; UL=Upper limb; W=Week; WST=Walking Speed Test.

a Assessments should be performed before the AbobotulinumtoxinA injection (if scheduled on an injection day).

a Cycle 1: The investigator decides if the subject is still responding to treatment or if a further AbobotulinumtxinA injection is needed, based on his/her clinical judgement. At Week 12, if a second injection is given, this marks the start of Cycle 2; if a second injection is not given, the subject returns at Week 20, if a second injection is given, this marks the start of Cycle 2; if a second injection is not given, the subject returns at Week 20, if a second injection is given, this marks the start of Cycle 2; if the investigator decides that a second injection should not be given, based on his/her clinical judgement, the subject will be withdrawn from the study.

Injection 2 will be performed at the Week 12, Week 16 or Week 20 visit after Injection 1, at the discretion of the investigator, based on his/her clinical judgement

d Cycle 2: The investigator decides if the subject is still responding to treatment or if a further Abordulinumtoxina. An injection is needed, based on his/her clinical judgement. At Week 12, if a further injection is needed, the subject completes the study after study assessments have been performed (before the injection is given) (i.e. Final Visit); if a further injection is not needed, the subject or stull visit); if a further injection is needed, the subject completes the study after study assessments have been performed (before the injection is given) (i.e. Final Visit); if a further injection is not needed, the subject completes the study after study after study assessments have been performed (before the injection is given) (i.e. Final Visit); if a further injection is not needed, the subject completes the study after study after study assessments have been performed (before the injection is given) (i.e. Final Visit); if a further injection is not needed, the subject completes the study after study

e For all subjects attending the Week 20 visit (Cycle 2), this will be the Final Visit

f Informed consent must be obtained before the subject undergoes any study-specific procedures.

g Demographics: sex and date of birth; race and ethnicity will also be collected if permitted according to local regulations

- h Disease history: date and type of ABI, date of spasticity development.
- Record all details of previous GSC or physiotherapy within 4 months before Baseline...

j Record if subject is naïve or non-naïve to BoNT treatment; if non-naïve to BoNT treatment, record dates of the first injection and last injection, which limbs were injected, and BoNT brand and dose used in the last injection.

k Medical history: any significant past or ongoing medical or surgical conditions (not related to UL or LL spasticity).

1 Prior and concomitant medications for UL or LL spasticity: therapies taken from 4 weeks prior to baseline through the study (including the subject's last study visit).

m Prior and concomitant medications and nondrug therapies: therapies taken from 4 weeks prior to baseline through the study (including the subject's last study visit).

n Urine pregnancy test: recorded for females of childbearing potential only.

o Measured at Baseline Visit, second injection visit and Final Visit, only (or early withdrawal). Vital signs: diastolic and systolic blood pressure and heart rate measured in the supine

position after 5 minutes rest. Weight will be measured at baseline, second injection and last visit; height will be measured at baseline only

p To be performed at the Final Visit (which may be Week 12, Week 16 or Week 20 after Injection 2) or early withdrawal.

q AROM is measured in each muscle group of the UL and LL (irrespective of whether injected or not).

r WST is to be performed in the same condition as at Baseline Visit, for example, if a cane was used at the Baseline Visit, the same cane should be used for this test at other visits.

s The number of days when GSC therapy was not performed since the last visit, as recorded in the subject diary, will be counted and recorded in the eCRF.

t To be performed only at the last postinjection FU visit after Injection 1 (i.e. the visit where second injection is performed, which may be Week 12, Week 16 or Week 20).

u AbobotulinumtoxinA (Dysport) (total dose 1500 U) will be administered by i.m. injection in the subject's UL and LL, according to the dose split decided by the investigator, according to his/her clinical judgement, based on which limb was considered the primary TT limb at the Baseline Visit and prespecified limits.

v Only for subjects who had GSC previously

#### CONFIDENTIAL

#### SAP Version 2.0: 05 October 2018

22/70

[figure not shown]

Table 2 **Summary of Re-injection Scenarios** 

b Injection 2 given at Week 12 relative to Injection 1, with 3 postinjection FU visits at Weeks 6, 12 and 16 relative to Injection 2

Injection 2 given at Week 12 relative to Injection 1, with 4 postinjection FU visits at Weeks 6, 12, 16 and 20 relative to Injection 2.

d Injection 2 given at Week 16 relative to Injection 1, with 2 postinjection FU visits at Weeks 6 and 12 relative to Injection 2.

Injection 2 given at Week 16 relative to Injection 1, with 3 postinjection FU visits at Weeks 6, 12 and 16 relative to Injection 2.

Injection 2 given at Week 16 relative to Injection 1, with 4 postinjection FU visits at Weeks 6, 12, 16 and 20 relative to Injection 2.

Injection 2 given at Week 20 relative to Injection 1, with 2 postinjection FU visits at Weeks 6 and 12 relative to Injection 2. g

Injection 2 given at Week 20 relative to Injection 1, with 3 postinjection FU visits at Weeks 6, 12 and 16 relative to Injection 2. Injection 2 given at Week 20 relative to Injection 1, with 4 postinjection FU visits at Weeks 6, 12, 16 and 20 relative to Injection 2.

#### 1.3.4 Planned sample size

The sample size was determined based on the primary efficacy endpoint (percentage of responder subjects at Week 6 after the second injection according to composite AROM). A 60% response rate was assumed based on previous studies (adult UL/LL) with an additional benefit of +10% compared with that observed in these studies (approximately 50% response rate at Week 4 of Cycle 2). The aim of this study will be to estimate this proportion with an accuracy of  $\pm 8\%$ . Given a twosided 95% confidence interval (CI), 145 subjects are required; with an assumed 5% dropout rate, 153 subjects will have to be enrolled to achieve a target of 145 evaluable subjects (i.e. subjects included in the Modified intent-to-treat (mITT) population). These calculations have been performed with nQuery using CI for proportions and assuming normal approximation.

#### 2 SUBJECT POPULATIONS (ANALYSIS SETS)

#### 2.1 **Enrolled** population

The enrolled population is all subjects who signed the informed consent.

#### 2.2 Efficacy

#### 2.2.1 Intention-To-Treat population (ITT)

Two ITT populations will be defined: one for the interim analysis and one for the final analysis.

- The ITT population for the interim analysis is all subjects who were injected at least once with the study treatment and for whom a primary Target Treatment limb has been defined.
- The ITT population for the final analysis is all subjects who were injected at least once with the study treatment, who received at least one day of GSC therapy during the study and for whom a primary Target Treatment limb has been defined.

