10 STATISTICS

10.1 Analyses Populations

The following populations will be used during the statistical analyses:

- Screened population: all subjects screened (i.e. who signed the informed consent).
- Safety population: all subjects who received at least one dose of study medication.
- **Intent-to-treat (ITT) population:** all subjects who received at least one dose of study medication. The ITT population will be identical to the safety population and will be denoted throughout as safety/ITT population.
- **Modified intent-to-treat (mITT) population:** all treated subjects having the primary efficacy outcome assessed at Week 6 after the second injection.
- **Per protocol (PP) population:** all subjects in the mITT population for whom no major protocol violations/deviations occurred.

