10.4.5 Efficacy Evaluation

10.4.5.1 Primary Efficacy Endpoint

As indicated in Section 7.1, the primary efficacy endpoint is as follows:

• the percentage of responder subjects at Week 6 after the second injection, according to composite AROM in the primary TT limb.

Composite AROM (X_A), regardless of whether the muscle groups were injected or not, as measured by goniometer in the primary TT limb (either UL or LL, depending on which one has been selected as the primary TT limb), will be calculated as follows:

- composite X_A UL: X_A UL = X_{AEF} + X_{AWF} + X_{AFF}
- composite $X_A LL$: $X_A LL = X_{Asol} + X_{AGN}$

where for UL: EF=elbow flexors, WF=wrist flexors and FF=extrinsic finger flexors, and for LL: Sol=soleus and GN=gastrocnemius muscles.

Definition of a responder: a subject will be considered a responder if he/she achieves at least the predefined improvement threshold - larger or equal to 35° in UL or 5° in LL - in the primary TT limb (based on the composite AROM individual change from baseline to Week 6 after the second injection).

PROTOCOL FINAL (INCLUDING AMENDMENT #2): 24 JANUARY 2018

Primary Efficacy Analysis of the Primary Efficacy Endpoint

The primary efficacy endpoint will be summarized descriptively as a binary variable using the mITT population.

Secondary Efficacy Analysis of the Primary Efficacy Endpoint

The following analyses will be conducted in support of the primary efficacy analysis.

The primary efficacy analysis will be repeated using the safety/ITT population where subjects with missing responder status at Week 6 after the second injection will have their last postbaseline responder status used instead. Subjects with no postbaseline responder status are considered nonresponders.

Additionally, the primary efficacy analysis will be repeated based on the PP population.

Exploratory Analysis of the Primary Efficacy Endpoint

The odds ratio for the primary efficacy endpoint and its associated two-sided 95% CI will be estimated from a logistic regression model with primary TT and country as fixed factors and composite AROM value at baseline as covariate. Further details will be provided in the SAP.

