# *1.3.2.1.4.3* Subject compliance with the GSC

As part of the GSC, the subjects will be given a diary at the Baseline Visit. They will be asked to record in this diary each day whether they have performed the GSC therapy. At each post-baseline FU visit, subjects will bring the GSC diary. The investigator will count the number of days when GSC therapy was not performed since the last visit and will record this in the eCRF.

Using the total number of study days and the total number of days when GSC therapy was not performed, the number of days when GSC was performed will be calculated. This will be used to determine the percentage subject compliance with GSC therapy.

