# 2.2.2 Modified intention-to-treat population (mITT)

The mITT population is all subjects who were injected at least once with the study treatment, who received at least one day of GSC therapy during the study, for whom a primary Target Treatment limb has been defined and who have the primary efficacy outcome assessed at Week 6 after the second injection (i.e. Visit 6).

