# 3.2.1.1.2 Secondary efficacy analyses of the primary efficacy endpoint

A frequency table of the percentage of responder subjects at Week 6 after the second injection will be provided on the ITT population (including the two-sided 95% CI) where subjects with missing responder status at Week 6 after the second injection will have their last postbaseline responder status used instead. Subjects with no postbaseline responder status will be considered nonresponders. The number of imputed data and the number of missing data will be provided.

The time to first response will be defined as the time elapsed from the date of first injection in the study to the date of first response (response as defined in section 3.2.14). For subjects who have a nonresponder status until the last study visit or for dropouts and lost to follow-up subjects, their data will be censored at the time of their last study visit.

The time to first response will be analysed using the Kaplan-Meier (KM) survival analysis method on the ITT population. The median survival time and the 95% CI of the median will be estimated using KM product-limit estimation. The time to first response will also be illustrated graphically using KM's estimates to display the cumulative rate of first response with the number of subjects at risk.

The following SAS® code will be used:

PROC LIFETEST data = ADTTE(where = (ittfl="Y")) METHOD=km;

TIME aval\*cnsr(1);

RUN;

Additionally, a frequency table of the percentage of responder subjects at Week 6 after the second injection will be provided on the PP population with the two-sided 95% CI.

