#### 5 CHANGES FROM PROTOCOL

- The screened population defined in the protocol will be replaced by "Enrolled population" with the same definition.
- Protocol stated that the ITT population will be identical to the safety population. However, two ITT populations will be defined: one for the interim analysis, which corresponds to the safety population, and one for the final analysis.
- The description of the AROM (degrees) against each muscle group (separately for injected muscle groups, not injected muscles groups and injected or not muscle groups), the composite AROM and the full composite AROM at baseline will be described by the following subgroups: country, primary TT limb, naïve or non-naïve to BoNT treatment and naïve or non-naïve to GSC.

- Protocol stated that the variable for the subject satisfaction with longer interval between 2 injections will be a Likert scale score. However, the possible answer to this question is: Yes / No / No opinion.
- Protocol stated that subgroup analyses will be provided for the primary efficacy endpoint by race (Asian / Black or African American / White / Native Hawaiian or Other Pacific Islander / American Indian or Alaska Native / Other) and ethnicity (Hispanic/Latino / Not Hispanic/Latino). As more than 90% of the subjects are represented in a single category for each variable, these subgroup analyses will not be performed.
- The analysis of the overall full composite AROM will be added.
- The analysis of concordance of the MFS between the local assessment by the investigators and the central review will be added.
- The analysis of the time to first response will be added.
- The analyses of the re-injection will be added: time to re-injection and moment of the re-injection in cycle 1.
- The analysis of the TEAEs of special interest will be added.

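### The SAP adds an undeclared GSC-day condition to the final ITT and mITT, and no planned table gives the Week 6/Cycle 2 responder rate on all injected subjects with missing status as nonresponse

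*SAP*

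**What the plan says.** **Populations.** Protocol 10.1 builds ITT on a single dose of study medication and states: "The ITT population will be identical to the safety population". Its mITT is "all treated subjects having the primary efficacy outcome assessed at Week 6 after the second injection". Neither definition mentions GSC days or a defined primary treatment target (TT) limb.

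SAP 2.2.1 restricts the final ITT to injected subjects "who received at least one day of GSC therapy during the study and for whom a primary Target Treatment limb has been defined". SAP 2.2.2 restricts mITT to injected subjects "who received at least one day of GSC therapy during the study, for whom a primary Target Treatment limb has been defined" who also have the Week 6/Cycle 2 outcome. mITT is the primary set (SAP 2.5).

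SAP Section 5 recalls the protocol's equation of ITT with safety and continues: "However, two ITT populations will be defined: one for the interim analysis, which corresponds to the safety population, and one for the final analysis". It names neither added condition and has no entry for mITT. It also equates the interim ITT with the safety population, although SAP 2.2.1 attaches the limb condition to that set too.

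**GSC data.** These are collected at follow-up visits: "The investigator will count the number of days when GSC therapy was not performed since the last visit" (SAP 1.3.2.1.4.3). SAP Appendix 1, items 9 and 25, derives days performed by subtraction.

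**Missing status at Week 6/Cycle 2.** On ITT, subjects without that status "will have their last postbaseline responder status used instead. Subjects with no postbaseline responder status will be considered nonresponders" (SAP 3.2.1.1.2). Protocol 10.4.5.1 has the same rule: "subjects with missing responder status at Week 6 after the second injection will have their last postbaseline responder status used instead".

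**Planned tables.** SAP Appendix 3 lists the Week 6/Cycle 2 responder outputs as mITT with subgroups, ITT with carry-forward, PP, and the mITT logistic model. None uses the safety population, and none counts every missing status as nonresponse.

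**The concern.** The study is single-arm and open-label, and its result is one proportion, so the denominator matters.

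First, having done at least one day of GSC is a fact that arises after injection. An injected subject who never returns has no GSC count. The nonresponder rule was written to keep such a subject in the ITT denominator; the population definition may remove the subject before that rule applies. Any such removal can only raise the ITT rate. The Week 6/Cycle 1 responder rate, also reported on ITT with missing status as nonresponse, would move in the same direction.

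Second, mITT by definition omits everyone who was not reinjected or not seen at Week 6 of Cycle 2. The one analysis that brings them back uses their last status. A subject withdrawn at Week 20 of Cycle 1 because the investigator judges a second injection unnecessary (Protocol 3.6) can therefore enter the rate after the second injection as a responder, on Cycle 1 data alone. The supportive ITT rate can then exceed the primary rate, and no planned table shows the lower bound.

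**Working it through.** **1. The plan's own figures.** Inputs from Protocol 10.2 and SAP 1.3.4: response 60%, half-width 8 points, two-sided 95%, dropout 5%.

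- n = 1.96² × 0.6 × 0.4 / 0.08² = 144.05, rounded up to 145. Reproduced.
- 145 / 0.95 = 152.6, rounded up to 153. Reproduced.

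The sample size is not in question. Below I take 153 injected (assuming everyone enrolled is injected), 145 assessed, 0.6 × 145 = 87 responders, and 8 without Week 6/Cycle 2 status.

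**2. Rates under each handling of the 8.** SAP 3.1.5 specifies Agresti-Coull intervals: n* = n + z², p* = (x + z²/2)/n*, limits p* ± z√(p*(1 − p*)/n*), with z² = 3.84.

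- mITT: 87/145 = 60.0%. n* = 148.84, p* = 0.597, half-width 0.079: 51.9% to 67.6%.
- All injected, missing as nonresponse: 87/153 = 56.9%. n* = 156.84, p* = 0.567, half-width 0.078: 48.9% to 64.4%.
- Carry-forward ITT, none of the 8 carried as responders: 87/153 = 56.9%.
- Carry-forward ITT, all 8 carried as responders: 95/153 = 62.1%.

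Carry-forward exceeds mITT once 5 of the 8 are carried as responders: 92/153 = 60.1%.

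The all-injected rate depends on the loss. At about 60% response among those assessed, and with assumed missingness of 10%, 15% and 20%, it is 83/153 = 54.2%, 78/153 = 51.0% and 73/153 = 47.7%.

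**3. Effect of the GSC condition on ITT.** Remove one unassessed nonresponder from 153.

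- Other 7 missing are nonresponders: 87/152 − 87/153 = 57.24 − 56.86 = 0.37 points.
- Other 7 carried as responders: 94/152 − 94/153 = 61.84 − 61.44 = 0.40 points.
- Two removed, lower case: 87/151 = 57.6%.

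The documents do not give the number of such subjects. Zero is possible.

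**4. Effect of the GSC condition on mITT.** Week 6 of Cycle 2 falls at the earliest nominally 84 + 42 = 126 days after baseline, following diary counts at the Week 6 and Week 12 visits of Cycle 1. A subject who reaches it with no GSC day at all is unlikely.

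**The case against.** Several counter-arguments have force.

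- **GSC is part of the treatment** (Protocol 1.6 and 3.1), so requiring some GSC among treated subjects is a defensible reading of mITT. This stands for mITT, though the protocol sets no minimum number of days and Section 5 should still say so. It does not carry to ITT, which the protocol ties to a dose of medication and to the safety set.
- **Carry-forward is the protocol's own rule**, the analysis is descriptive, and the number imputed is reported beside the ITT rate. All true. The missing table is a gap in the sensitivity analyses, not a departure from the protocol.
- **The rate can be rebuilt** from the mITT responder count and the safety N. Also true; what is lacking is a planned result with its interval.
- **Missing as nonresponse has its own bias**, because some subjects withdrawn at Week 20 of Cycle 1 may still be responding. Agreed: it is a conservative bound.

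A reader might infer more than the documents support.

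- *The SAP treats missing status differently in the two cycles.* SAP 3.2.1.2 counts missing Week 6/Cycle 1 status as nonresponse, but that is the first postbaseline analysis visit (SAP Table 1; windows in SAP 3.2.15). Nothing earlier exists to carry forward, so the Cycle 2 rule applied there gives the same answer. The Cycle 1 rule is therefore no precedent for overriding carry-forward in Cycle 2.
- *GSC days cannot be derived.* Appendix 1 does derive them. Only subjects with no follow-up GSC record are left undefined.
- *Section 5 conceals the ITT change.* It discloses a separate final ITT; it omits the conditions and the mITT change.

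**Conclusion.** Two minor points hold.

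1. The GSC-day and TT-limb conditions on the final ITT and mITT are absent from Protocol 10.1 and unnamed in SAP Section 5. The GSC condition may remove injected subjects with no follow-up record whom the ITT rule would count as nonresponders. The size is about 0.4 points per subject removed, for a number that is unknown and may be zero. The effect on mITT is probably negligible.
2. No planned output gives the Week 6/Cycle 2 rate on all injected subjects with missing status as nonresponse. At planned loss it would be 56.9% (48.9% to 64.4%), against 60.0% (51.9% to 67.6%) in mITT.

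It would be wrong to attribute the 60.0 − 56.9 = 3.1-point gap to the GSC condition. It comes from how missing status is handled, and it lies inside the planned ±8 points.

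The figures assume that all 153 enrolled subjects are injected, that 5% are lost and that 60% of those assessed respond. The 56.9% floor for carry-forward also assumes that the GSC condition removes no assessed subject; losing one assessed responder would allow 86/152 = 56.6%.

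**What to change.** - **Final ITT:** delete the GSC condition, in line with the protocol.
- **mITT:** delete the GSC condition, or list it in Section 5 with a reason and say how it is determined.
- **TT-limb condition:** list it in Section 5 for every set to which it applies.
- **Unchanged:** mITT stays the primary set and the carry-forward ITT analysis stays.
- **New supportive table:** Week 6/Cycle 2 responder rate on all injected subjects, missing status counted as nonresponse, with the Agresti-Coull interval. State that the denominator is all injected subjects, since SAP 3.2.16 otherwise leaves missing values out of denominators. Show the number missing by reason, with subjects withdrawn at Week 20 of Cycle 1 because no second injection was judged necessary on a separate line.

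The cost is SAP wording and one table from data already collected. The new rate will be equal to or lower than the mITT rate and must be labelled a conservative bound, because some of those Week 20 withdrawals may still be responding.
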